2.2. Obesogenic Environment

Individual's behaviours are influenced from obesogenic environments considered those that promote high-energy food consumption and limit the opportunities for spending that energy (Powell, Spears and Rebori, 2010). The high prevalence of overweight and obesity in early ages is can be partially explained by changes in eating and physical activity behaviours associated with an obesogenic environment (Swinburn, Egger and Raza, 1999; Safron *et al.*, 2011). Multiple conditions in the children's environment could positively or negatively influence the risk of being overweight or obese (Hesketh and Campbell, 2010). There is a consensus that also genes, biology, and individual behaviour cannot fully explain the rapid increase in childhood obesity (Sallis and Glanz, 2009).

Obesogenic environments promote a high-caloric intake in different forms including the widespread advertising of foods high in fat, sugar, and salt targeting children and adolescents; inadequate nutritional guidance for the population as well as the limited availability and accessibility of healthy food and beverages in school settings (Sallis and Glanz, 2009; Powell, Spears and Rebori, 2010). In addition, these environments limit the access to adequate physical activity facilities including road insecurity and high-rate of crime, which contribute to a significant decrease in the percentage of children who are physically active and with healthy body composition (Sallis and Glanz, 2009).

School is an ideal place for health promotion and obesity prevention since is where schoolchildren spend a large proportion of their time. The school provides curricular (e.g. physical education course, PE), and extracurricular (e.g. recess, tournaments, active transport) opportunities to learn and practice healthy habits (De Bourdeaudhuij *et al.*, 2011). Although interventions focused on the adoption of healthy lifestyles in schools have shown inconsistent results, they seem to be promising options to contribute to the prevention of obesity among schoolchildren (Brown and Summerbell, 2009).

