7.1. Design analysis

The design analysis of Salud Escolar will be conducted through a desk-review and semi-structured interviews (if necessary). The information derived from this analysis will (1) facilitate decision-making processes to improve the internal logistics of Salud Escolar, and (2) facilitate the understanding of how Salud Escolar may contribute to solve the target health problem.

Several meetings will be held between the research team and the technical team of Salud Escolar in order to define key aspects of the methodology, such as the documents to be reviewed and the key actors to interview (if necessary), as well as for the review, discussion, and socialization of the preliminary results. The analysis will be carried out from October to November 2019 through the following phases:

Desk-review

Administrative records, databases, documents and public documentation related to Salud Escolar will be gathered. Additional information or documents considered as relevant by Salud Escolar technical team will be included. An adaptation of CONEVAL's design evaluation Terms of Reference (TOR) will be used as an instrument to conduct the desk-review (Table 2). In addition, references from the United Nations Children's Fund (UNICEF) will be considered to include a gender perspective during the analysis (Table 3). This approach considers the differences in roles and responsibilities attributed to women and men, girls and boys (UNICEF South Asia, 2018).

Three main documents have been considered for the desk-review to answer the questions of CONEVAL's instrument (Table 2): 1) Document Salud Escolar: Escuelas Saludables y Activas, 2) Program diagnostic and supervision instruments, 3) results of other international school-based programs that have been successful in promoting healthy habits in children and adolescents. Additionally, the following documents could be considered as well:

- General guidelines for the sale and distribution of prepared and processed foods and beverages in the schools of the National Educational System (Diario Oficial de la Federación, 2015a).
- Official Mexican Standard NOM-251-SSA1-2009, Hygienic practices for the process of food, beverages or supplements (Diario Oficial de la Federación, 2015a).
- Official Mexican Standard NOM-043-SSA2-2005, Basic health services. Promotion and education for health in nutrition. Criteria for providing guidance (Diario Oficial de la Federación, 2005).

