- General guidelines for the installation and maintenance of drinking fountains in the schools of the National Educational System (Diario Oficial de la Federación, 2015b).
- Official Mexican Standard NOM-201-SSA1-2002, Products, and services. Water and ice for human consumption, loose and packaged (Diario Oficial de la Federación, 2002a).

- Official Mexican Standard NOM-230-SSA-2002, Environmental Health. Water for human use and consumption, sanitary requirements that must be met in public and private supply systems during water management (Diario Oficial de la Federación, 2002b).
- Guidelines for the Comprehensive Strategy for Food Social Assistance - School Breakfasts (Secretaría de Salud, 2019).

CONEVAL's instrument includes questions with dichotomous response options (YES / NO), which should be supported by documentary evidence. When the answer is YES, one of the four levels of response defined for each question will be selected (https://www.coneval.org.mx/Evaluacion/MDE/Documents/TDR_Disenio.pdf) considering the adaptations made by the evaluation team (Table 2). Questions that do not have binary answers (do not include response levels) should be answered based on the desk-review and providing a rationale for the response. Each question will be answered in a maximum of one page. The following concepts will be included: a) the question, b) the binary (YES / NO) or open answer (as appropriate), and c) the analysis that justifies the answer. When the characteristics of Salud Escolar do not allow answering a specific question, the option "Does not apply" will be also available requesting an explanation of this.

Table 2 Research questions contained in the CONEVAL's instrument

Section	Questions
Creation of program creation and design	
Is the priority problem or need that the program seeks to solve identified in a document?
 
Is there any diagnosis of the problem that the program is aiming to address?
 
Is there theoretical or empirical evidence that support the type of intervention in the program?
 
Does the program have a theory of change?
 
Is there evidence that a formative research has been carried out whose results have been contemplated in the program design?

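### The desk review names only successful programmes as its outside evidence of effect, and nothing asks for null or negative evaluations

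*Combined protocol and SAP*

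**What the plan says.** Section 7.1 (Desk-review) names three main sources for the Table 2 questions: the programme document, the programme's diagnostic and supervision instruments, and "results of other international school-based programs that have been successful in promoting healthy habits in children and adolescents".

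A further list is introduced with "Additionally, the following documents could be considered as well". Its seven entries are Mexican guidelines and official standards on food sales, hygiene, nutrition guidance, drinking fountains, water and school breakfasts. There is one more route: "Additional information or documents considered as relevant by Salud Escolar technical team will be included". The same section says that meetings between the research team and that technical team will settle which documents are reviewed.

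Table 2 contains the item that depends on this evidence: "Is there theoretical or empirical evidence that support the type of intervention in the program". On the answer format, the plan states: "CONEVAL's instrument includes questions with dichotomous response options (YES / NO), which should be supported by documentary evidence". It adds: "When the answer is YES, one of the four levels of response defined for each question will be selected". The levels are set out in an external CONEVAL document, with adaptations by the evaluation team. Each answer must also carry a written analysis that justifies it.

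On the wider evidence, a sentence in Section 2.2 begins "Although interventions focused on the adoption of healthy lifestyles in schools have shown inconsistent results" and goes on to call such interventions promising. Section 5 says that multi-component, prevention-focused school programmes usually work, and cites systematic reviews.

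**The concern.** The third source is defined by outcome. A reviewer who follows the list literally looks up programmes that worked and does not look up comparable programmes that did not. By the protocol's own account in Section 2.2 the record is mixed, so less favourable results exist to be found.

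This also sits badly with the purpose set out in Sections 3.3 and 3.4. There, policy analysis is meant to be systematic and objective and to learn from failure as well as success, and design analysis is meant to help judge whether the proposed actions are likely to solve the problem. A set made up of successes cannot inform that likelihood.

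What is at stake is the credibility of one answer in the design analysis and of the recommendations that lean on it. Table 9 lists a design report and recommendations for improving the programme as Stage 1 deliverables, and Section 2.3 plans expansion to 14 states and then nationwide. Section 2.3 also lists INSP among the programme's developers, and Section 7.1 assigns the desk review to INSP researchers. That is no sign of bad faith, but it makes a source rule that is neutral to results more valuable.

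**Working it through.** The plan gives no figure to reproduce. The check sets the passages side by side and reasons from them.

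**1. Which named sources are outside evidence of effect?**

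| Source (Section 7.1) | Outside the programme? | Evidence of effect? |
|---|---|---|
| Programme document | No | Not an outside source |
| Diagnostic and supervision instruments | No | No |
| Results of international programmes | Yes | Yes, limited to successful ones |
| Seven optional guidelines and standards | Yes | No, they are normative texts |
| Documents the technical team finds relevant | Open | Open; no rule asks for unfavourable results |

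The interviews in Table 4 (4 + 4 + 2 = 10 key actors from health, education and DIF) concern how the programme was designed. They do not supply effectiveness results.

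**2. How many Table 2 questions depend on it?** Counting by section: creation and design 5, national goals 3, population 1, beneficiaries 2, indicator matrix 11, budget 3, complementarities 1. The total is 5 + 3 + 1 + 2 + 11 + 3 + 1 = 26. One asks directly about outside evidence of effect: 1/26, or about 4%. Most of the rest concern the programme's own diagnosis, populations, indicators and budget.

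**3. What does selection on success do to that item?** Let S be the number of comparable programmes with supporting results and N the number with null or negative results.

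- Read as an existence question, the empirical part is YES when S ≥ 1. N does not enter, so the YES or NO is the same for the success-only set and for the full set. Theory alone can also satisfy the item.
- Read as a question of balance, the supporting share is S/(S + N) in the full set. In the success-only set it is S/S = 100%, whatever N is. This is where information is lost.

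The restriction therefore leaves the literal YES/NO answer alone and distorts the picture of the evidence in the written justification.

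**4. Can successes alone show which components matter?** No. That needs a component's frequency among successes and among failures, and with no failures in the set the second cannot be estimated. No Table 2 question asks for this comparison, so it counts against recommendations that rest on such reasoning and not against a planned analysis.

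**5. Do Sections 2.2 and 5 resolve the matter?** They differ in tone: inconsistent results in one, usual success for multi-component programmes in the other. If Section 5 is right, a set chosen without regard to result will show it. If it is too favourable, the present source would not reveal that.

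**The case against.** The strongest reply has four parts.

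**The list is open.** Nothing bars null evaluations; the technical team can add documents, and the documents are to be agreed in meetings. This stands. A reader might infer that unfavourable studies are excluded by rule, and the text does not say so. What remains is that nothing calls for them, and that the relevance judgement for additions lies with the team of the programme under review.

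**The evidence item is permissive in itself.** A reader might infer that the choice of sources is what makes NO almost impossible. The documents do not support that: the item asks whether supporting theory or evidence exists, and a balanced set would often give YES as well. Nor can inflation of the four-level grade be shown, because the level criteria are not in the documents.

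**The reach is small.** A reader might infer that the whole answer to research question 1 is tilted toward endorsement. With one item in 26, interviews intended to complement the desk review, triangulation, and a SWOT table that must list weaknesses and threats, that does not follow.

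**Successful programmes are a natural benchmark.** Section 9 foresees comparing the programme's strategies with evidence-based interventions, and such a comparison can expose missing components. This is a fair use, but it does not remove the defect, because Section 7.1 assigns the source to answering the Table 2 questions, and the evidence item is one of them.

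**Conclusion.** The point holds in limited form. The only outside evidence of effect named for the desk review is selected on its result, and no provision asks for contrary results. This conflicts with the protocol's own description of the field and of what policy analysis is for.

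Its size is modest: mainly the justification of 1 of 26 Table 2 answers, and any recommendation that draws on it. No numerical bias can be given, because the documents do not say what share of comparable programmes failed. The difference-in-difference impact analysis in Section 7.3 does not use this source and is unaffected.

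Two assumptions underlie this: that the description of the third source is meant as a selection criterion and is not just loose wording, and that null or negative evaluations would not reach the review by the open route for additional documents. If either is wrong, the practical effect is smaller, but the text would still need correcting. The change is worth making because it is specific and cheap.

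**What to change.** In Section 7.1 (Desk-review), replace the third main source with results of evaluated school-based programmes chosen by comparable population and components, whatever their result. Systematic reviews with stated search and inclusion rules, such as those already cited in Sections 2.3 and 5, are an efficient way in.

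In the justification of the Table 2 evidence item, report supporting and contrary results separately for diet, hydration and physical activity. Successful programmes may still be used as a benchmark if that use is labelled as such.

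The cost is some extra reading within a desk review that is already planned, with no fieldwork. If the review (scheduled for October to November 2019) has been completed, its answer to this one item can be supplemented on the same basis.

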7.2 Short-term results analysis (baseline measurement)

The results of Salud Escolar will be estimated by measuring changes in knowledge, attitudes, and practices related to correct nutrition, adequate hydration and physical activity. The Health and Nutrition Questionnaire, prepared by the Ministry of Health, will be used. This questionnaire has two versions [for 3rd grade of primary school (Appendix 3); and for 4th to 6th grade (Appendix 4) and consists of 3 main sections (Figure 6).The questionnaires were previously used in the Health in your School program. Data collection will be conducted by the Ministry of Health and the INSP research team will be solely responsible for data analysis.

Sample

The questionnaire is addressed to all girls and boys from 3rd to 6th grade (n = approximately 20,000 girls/boys) of the 58 primary schools selected for the implementation of the first phase of Salud Escolar. As part of Salud Escolar, staff from the Ministry of Health will go to the schools on the first day and give teachers a diptych announcing the Program, actions, and objectives (Appendix 5) and informed consent for parents. Teachers will send these documents in children's backpack and parents will review and return the signed consent (if given) on the next day.

Data collection

The Ministry of Health staff will apply the questionnaires with the support of the teaching staff. The questionnaires will be administered indoors (e.g. classroom) during school hours. Children whose parents have given their consent to participate will be included and children's oral assent will be obtained.

Data processing and analysis

Data will be coded by the Ministry of Health staff using an automated system and the database will be given to the INSP research team for subsequent analysis. A descriptive analysis of the data will be carried out, estimating means standard deviations for the continuous variables and proportions (%) for the categorical variables. Likewise, all available information will be disaggregated by sex and age.

[figure not shown]

Figure 7 Sections included in the Health and Food Questionnaire

7.3 Impact analysis (baseline measurement)

Considering that Salud Escolar aims at creating healthy school environments, the impact analysis will be focused on the evaluation of some individual and environmental indicators.

Study design

A quasi-experimental design with baseline and endline evaluation will be used in schools where the School Health Program will be implemented (intervention group), and in schools where the program will not be implemented (control group). Measurements will be made prior to the start of the school program (pre-intervention), and 10 months after its implementation (post-intervention).

Study hypothesis

Based on similar studies previously carried out in the school population (Carriedo *et al.*, 2013; Safdie, Jennings-Aburto and Lévesque, 2013; McKenzie, 2015), we hypothesized the following changes in the endline measurement among children exposed to Salud Escolar, in comparison with those in the comparison group (not exposed to the intervention program):

- water consumption will increase by 171 ml (Carriedo *et al.*, 2013),
- time engaged in MVPA will increase in total 10 minutes per day, with an increase of 4 minutes per day during school recess and 4 minutes per day during physical education classes (Haerens *et al.*, 2007),
- the percentage of girls/boys who consume fruits and vegetables daily in the school environment will increase by 6.7% (Safdie, Jennings-Aburto and Lévesque, 2013).

Sample size calculation

The impact analysis study will be carried out in 30 primary schools in Mexico City (Intervention group = 15; Control Group = 15). The number of schools included was defined to better identify the effect (with a small number of schools the effect of the intervention could be confused with the characteristics of the schools) (Soto-Estrada *et al.*, 2016). Other criteria considered were the short time available for data collection (no more than three months according to reports by the Ministry of Health based on their experience during the implementation of the Health in your School program), as well as the available funds.

Table 6 presents the sample size necessary for hypotheses testing, considering a significance level of $\alpha = 0.05$, a statistical power of 80%, and a correlation of 0.2 between the basal and final measurements. Considering that the largest sample size required is the one to estimate the effect of the intervention on fruit and vegetable consumption ($n = 388$), a design effect of 2, and 20% losses to follow-up, it is estimated that a total of 980 girls and boys ($n = 490$ per intervention group) are needed.

A baseline measurement of 1000 girls and boys has been proposed. Considering the same assumptions of design effect and loss to follow-up, it was estimated that a sample size of 595 girls and boys is required for accelerometry measurements and the System for Observing Fitness Instruction Time (SOFIT).

Table 6 The sample size required to estimate expected differences

Indicator	Standard deviation	Expected difference	Sample size
Water consumption (ml/day)	631	171	384
MVPA (min/day)	40	10	248
MVPA (min/PE)	9	3.8	248
MVPA (min/recess)	12	3.9	244
Fruit and vegetable consumption (% of schoolchildren)		6.2%	388

Note. MVPA= moderate to vigorous physical activity; PE= physical education.

Schools selection

The intervention group schools will be selected randomly from the predefined list of 58 schools selected by the Ministries of Health and Education to participate in the first phase of implementation of Salud Escolar. The control group will be selected from a list of schools available in Mexico City provided by the Ministry of Education, where the program will not be implemented. Given that the selection of the 58 schools of the intervention group will not be at random, schools from the control group will be as similar as possible to those in the intervention group. Thus, it will be sought that the schools of both groups (i.e, intervention and comparison) are paired based on the following characteristics:

- Location: schools should be in the same geographical area < 5 km.
- Basic Geostatistical Area (BGA): within a similar BGA level
- Type of working day: in the same type of working day (regular, extended or full time)
- Hours: both in the morning or in the afternoon
- Size: schools from both groups will be expected to have a similar number of students and classes.

Participants

For the evaluation of the individual indicators, boys and girls from 1st to 6th grade of primary school will be selected at random from the attendance lists of the school groups. A written consent from parents will be requested (Appendix 6) and an assent from the participants (Appendix 7). In the case of the evaluation of environmental indicators in schools, all schools' principals will be invited to participate and a written consent will be requested (Appendix 8).

Inclusion and exclusion criteria for schools and participants

Students who have provided assent to participate and who have the informed written consent of parents or caregivers will be eligible. Children who have a physical or mental disability to participate the program will be excluded.

Measurements

Healthy diet. Two instruments will be used, a 24-hour recall to estimate the total diet of schoolchildren, and food weighing to estimate food consumption within the school environment.

24-hour recall. This instrument will be used to measure and evaluate the total diet of schoolchildren. A 24-hour recall will be applied to mothers, fathers, or caregivers of participants responsible for feeding and preparing meals at home (Appendix 9). The registration system used for the National Health and Nutrition Surveys will be used (Shamah-Levy *et al.*, 2018). The 24-hour recall consists of an interview in which participants are asked to remember and describe all the food and beverages consumed the day before the interview, from the first intake of any food or drink, up to the last food or drink consumed before sleeping (Shim, Oh and Kim, 2014). The adult responsible for feeding the child will be asked to name, describe and quantify the amounts of all the food and drinks consumed by the participant the previous day. The information collected will include the characteristics of the food or drink, including preparation method, brands and quantity consumed (considering edible portion and total proportion consumed). Food and beverages consumed at school or outside the home without the adult being interviewed will be reported by schoolchildren. The instrument will be applied by trained staff and will be collected with the use of a laptop, using a software to collect 24-hour recalls in the Mexican population.

Since part of the objectives of Salud Escolar is to improve the quality of the schoolchildren's diet and reduce the consumption of highly processed foods, the information obtained from the 24-hour recall will be used to evaluate the consumption of fruits and vegetables, sugar sweetened beverages (SSBs), and highly processed foods. A comparison will be conducted between participants consumption against the recommendations established in the Dietary and Physical Activity Guidelines in the Context of Overweight and Obesity in the Mexican Population (Bonvecchio, 2015). The proportion of schoolchildren who consume fruits and vegetables, and ultra-processed foods as outcome variables will be estimated.

Food and drink consumption during recess. Trained staff will record the food and drinks consumed during recess (snack or lunch) to objectively measure food consumption at school. Schoolchildren will be asked to show their lunch and beverages (brought from home or purchased at school) and what is contained will be recorded and weighted. This process will allow the detailed recording of the consumption of food and beverages at school campus, and the evaluation of the changes in food and beverages brought from home and purchased at school.

Correct hydration.

To analyze the impact of Salud Escolar on water consumption, a Beverage Diary will be applied to participants from 3rd to 6th grade (Appendix 10). The diary has been previously used and validated in different studies carried out by the INSP among schoolchildren (unpublished data) (Safdie *et al.*, no date; Pérez, 2016). Participants will receive a hard copy of the diary and will be asked to complete it at

home during three days. Data will be coded in Excel format and the consumption of water and SSBs (ml/day) will be estimated based on previously standardized procedures (Salud, 2015).

Physical activity

Direct observation and accelerometry will be used to measure physical activity.

Direct observation. This will be used to analyze the effect of Salud Escolar on the quality of physical education (PE) classes and active recess of the program (minutes of MVPA). The System for Observing Fitness Instruction Time (SOFIT) will be used to evaluate PE and an adapted version will be used to measure physical activity during recess. SOFIT is a comprehensive tool for evaluating physical education in terms of student physical activity levels, class context, and teacher or instructor behavior (McKenzie, 2015). This is a validated and reliable tool, which can be used in multiple contexts (McKenzie, 2015). Prior to the start of the lesson, target students will be selected. One student will be observed for 4 minutes, then the observer will focus on the other remaining students for 4 minutes (each) until class ends. Prerecorded verbal prompts on CDs, MP3s, or audiotapes will be used to help the observer to systematically follow up the class on a 10-second intervals basis throughout the class. During each registration interval, the observer records a code corresponding to the behaviors of interest (students, context, or teacher).

All data will be recorded in a specific format for subsequent analysis (Appendix 11). Data will be summarized by time (3 intervals = 1 minute), percentage of intervals or class time, or estimated energy expenditure. Comparisons may be made between different categories, between classes over time, or against established standards. The main variables to obtain from this observation method are:

- The physical activity levels of students: Minutes and % of the PE class in each of the intensities of physical activity (including minutes of MVPA), energy expenditure estimated per session (kcal/kg) and rate of the estimated energy expenditure (kcal/kg/min) (Department of Health & Human Services, 2018).
- Physical education schedule: frequency of sessions and adherence to the proposed schedule, scheduled duration and actual duration of the sessions.
- Context of the session: minutes and % of the session time spent in administrative matters, instruction, physical fitness, skill exercises, play time and others.
- Teacher behavior: % of the class that the teacher or instructor invests in promoting the activity during and outside of class time.

Accelerometry

Actigraph GT3X + accelerometers (ActiGraph, LLC, Pensacola, FL, USA) will be used to assess the effect of the intervention on total physical activity (minutes per day of MVPA). Accelerometry is a method for objectively monitoring physical activity and providing rich data about users' physical activity intensities. Accelerometers will be distributed to a subsample of participants in schools by

trained staff who also will record allocation and collection of the devices (Appendix 12).

Participants will be asked to wear an accelerometer with a flexible belt, on the right side at the axillary midline, for at least 7 full days (plus one day of familiarization and the morning of the last day), including two weekend days. Wearing time will be at least for 7 days in order to maximize the number of participants with sufficient valid data (minimum wearing time of 4 days with 10 hours each day). Participants and their parents or caregivers will be explained to remove the accelerometer only during bedtime and water-based activities (e.g. swimming), clear information and a demonstration of wearing the device will be provided by trained staff (Appendix 14). To ensure the adequate use of accelerometers, a daily checklist (Appendix 13) will be used to record the use of the accelerometer every morning at the school by trained staff. This school visits will be an opportunity for the trained staff to clarify participants questions about the accelerometer. Phone messages and calls, and small incentives (stickers) at the time of verification by the staff will be used as compliance enhancing strategies.

The software ActiLife 6.13.4 will be used for accelerometer initialization prior to allocation and data download after collection. Daily MVPA will be estimated using an algorithm prepared by the research team. Freedson's cut-off points will be used to estimate the schoolchildren time per day spent at different intensities of physical activity (Department of Health & Human Services, 2018).

Other variables

Anthropometry

Weight and height will be measured in the whole sample (Hernández and Rivera, 2006).⁹⁶ Weight will be used as an indicator of total body mass and will be measured using portable scale with an accuracy of ± 200 g. The scale will be placed on a flat surface in vertical line to a wall, at a 90-degree angle. The weight will be recorded with the participant standing in the central part of the scale, behind the wall, in a straight position (barefoot, with heels together, toes slightly apart and arms hanging parallel to the axis of the body). Participants should be barefoot and in light clothing (no sweater or objects in the bags) during weight measurement.

Height will be used as an indicator of schoolchildren linear growth. A stadiometer will be used to measure height. This consists of a flexible metal measuring tape with a length of 2 m and a portable square that is placed on a right wall at a 90-degree angle with the floor. The height will be measured in a straight position with the back and head resting on the wall. Participants' heads will be oriented by looking for the Frankfort plane (horizontal line from the lower orbital end to the upper edge of the external ear canal that keeps the head parallel to the floor). Participants will be asked to remove their shoes and any objects on their head (e.g. pins, buns, high hairstyles). The size will be recorded to the tenth centimeter (0.1cm).

Socioeconomic status

The questionnaire from the Mexican Agency for Market Research Agencies (AMAI, by its Spanish initials) will be used to estimate the socioeconomic level of the family (Appendix 15) (AMAI, 2018). This questionnaire considers the following variables: 1) number of full bathrooms, 2) number of cars, 3) home broadband, 4) household income of more than 14 years, 5) average monthly salary (<\$ 2,699; \$ 2,700 - \$ 6799; \$ 6,800- \$ 11,599; \$ 11,600- \$ 34,999;> \$ 35,000). This model defines a total number of points for each of the items and uses a maximum score of 300 points that are distributed among 7 socioeconomic levels from A/B to E.

- A/B. The socioeconomic level A/B includes 82% of households in which the head of the family has professional studies, of these 98% of households have home broadband. In this level there is the highest investment in education (13%) and one with the lowest proportion spent on food (25%).
- C+. The 89% of households at this level have one or more transport vehicles and 91% have home broadband. Around 31% of their spending goes to food and 5% to footwear and clothing, which is, similar to other levels.
- C. The 81% of the households at this level have a head of household with studies higher than primary and 73% have home broadband. Of the total expenses of this level, 35% are destined to food and 9% to education.
- C-. In the 73% of households at this level have a head of household with studies above. Of these homes 47% have home broadband, 38% of the expenses is allocated for food, and 5% is for clothing and footwear
- D+. In 62% of households at this level, the head of the household has a higher education than primary. Only 19% have home broadband, 41% of the expenses is in food and 7% to education
- D. In 56% of households the head of the household has studies until primary school, 4% has home broadband, and 46% of the expending is in food.
- E. Most households at this level (95%) have a head of household with studies not higher than primary education and only 0.1 % have home broadband. The spending at this level allocated to food is 52%) and this is the group with the lowest proportion of spending dedicated to education (5%).

Environmental indicators

The School Audit Tool developed for the International Study of Childhood Obesity, Lifestyles and the Environment (ISCOLE) will be used to measure school environment (Broyles *et al.*, 2015). This tool has been found feasible and reliable to be applied in school contexts in different countries (Broyles *et al.*, 2015). The tool will be applied in the school of intervention and comparison groups. The School Audit Tool evaluates school policies and practices related to healthy eating and physical activity and will be carried out through direct observation and questionnaires applied to the school's administrative staff.

This tool was developed based on surveys from *The school administrator survey* (Council of Chief State School Officers, no date), from the "School Health Policies

and Practices” (SHPPS) study (Council of Chief State School Officers, no date), from the Health Behavior in School-Aged Children (HBSC) survey (Council of Chief State School Officers, no date), and from the School Health Environment Survey (SHES) (Kroeker *et al.*, 2006). The components of the School Audit Tool assessing the school's built physical environment were taken from the school audit tool of the Sport, Physical activity and Eating behavior: Environmental Determinants in Young people (SPEEDY) study showing acceptable validity and reliability (Jones *et al.*, 2010). The tool also includes items to characterize the school grounds, the aesthetics of the school, the supply of food and access to fast-food restaurants around the school, and the amount of class time spent on physical education (Appendix 16).

Data analysis.

For the baseline evaluation, a descriptive analysis of the sample is contemplated, estimating the means and standard deviations for continuous variables, as well as percentages for categorical variables. Descriptive variables will be estimated in the total sample and by study group. A consistency in the results from the research team and the characteristics of the schools reported in the School Audit Tool will be conducted, using paired t-tests for continuous variables and Chi-square tests for categorical variables. The statistical package Stata 14 will be used for data analysis which will be disaggregated by participants sex and age.

The impact of Salud Escolar will be estimated using a difference in difference analysis considering schools as clustering variables. Behaviors of interest will be the outcome variables and group allocation and time will be the independent variables. The effect of Salud Escolar will be tested by introducing an interaction term between time and group allocation.

Fieldwork

The fieldwork will be carried out by three teams of six members, three supervisors (one for each brigade) and a coordinator. In each team two members will apply accelerometry and anthropometry measurements, four will apply the beverage diary and the 24-hour recall. Each team is estimated to work within each school for approximately one week, which represent a total of 12 schools visited in a month and two and a half months for the full data collection at the baseline stage.

